**REGULATORY FRAMEWORK:**

Please indicate all that apply:

	DOD (Department of Defense)
	DOE (Department of Energy)
	DOJ (Department of Justice)
	ED (Department of Education)
	EPA (Environmental Protection Agency)
	FDA (Food and Drug Administration)
	HHS (Department of Health and Human Services)
	VA
	Other:

**FUNDING:**

The protocol is awaiting funding. An UNM HSC RAC Grant has been applied for.

**CLINICAL TRIALS**

Is this a clinical trial per the NIH definition of a Clinical Trial?  Yes  No

NIH Definition of a Clinical Trial:

A research study in which one or more human subjects are prospectively assigned to one or more interventions. An "intervention" is defined as a manipulation of the subject or subject's environment for the purpose of modifying one or more health-related biomedical or behavioral processes and/or endpoints. Examples include: drugs/small molecules/compounds; biologics; devices; procedures (e.g., surgical techniques); delivery systems (e.g., telemedicine, face-to-face interviews); strategies to change health-related behavior (e.g., diet, cognitive therapy, exercise, development of new

PROTOCOL TITLE: Piloting an MI Informed Shame Resilience Intervention

habits); treatment strategies; prevention strategies; and, diagnostic strategies (which may include placebo or other control) to evaluate the effects of those interventions on health-related biomedical or behavioral outcomes.

**Use the following four questions to determine the difference between a clinical study and a clinical trial:**

- 1) Does the study involve human participants?  Yes  No
- 2) Are the participants prospectively assigned to an intervention?  Yes  No
- 3) Is the study designed to evaluate the effect of the intervention on the participants?  Yes  No
- 4) Is the effect being evaluated a health-related biomedical or behavioral outcome?  Yes  No

Note that if the answers to the 4 questions are yes, your study meets the NIH definition of a clinical trial, even if...

- You are studying healthy participants
- Your study does not have a comparison group (e.g., placebo or control)
- Your study is only designed to assess the pharmacokinetics, safety, and/or maximum tolerated dose of an investigational drug
- Your study is utilizing a behavioral intervention

If yes to all 4 questions, please confirm that the research team is familiar with and agrees to comply with the investigator requirement to register the study on the ClinicalTrials.gov database. Additionally, the approved consent document(s) must be uploaded to the ClinicalTrials.gov database  Yes  No

For any assistance with registration of your trial or the requirements, please contact [[contact]](mailto:[contact])

## 1. Objectives

1.1 Shame is an emotion that can have significant negative impacts on health outcomes, including engagement in care. Feelings of shame are commonly experienced with stigmatized behaviors, such as substance misuse, and may be particularly strong among pregnant women who misuse substances. Rates of opioid misuse during pregnancy are dramatically rising, particularly in New Mexico, leading to negative health outcomes for mothers and fetuses. Shame has been found to decrease these patients' willingness to attend and engage in care. Although a theoretical model is available to guide interventions to reduce shame, it has not been tested empirically. In the current study, we seek to evaluate the preliminary effectiveness and feasibility of a brief Shame Resilience Intervention among women seeking care in UNM's Milagro program, a prenatal medical clinic for opioid using pregnant women. This research has the potential to significantly improve public health by generating a tool to reduce barriers to care.

The specific aims of this project are as follows:

### **Aim 1: Assess the feasibility of study methods (recruitment and retention), intervention fidelity, and treatment satisfaction.**

We will track rates of participation in the study as well as retention at follow-up. All intervention sessions will be audio-recorded and rated using the Motivational Interviewing Treatment Integrity tool. Participants will provide quantitative ratings of treatment satisfaction. In addition, a random sample of ten participants will be invited to complete qualitative interviews on treatment satisfaction.

Hypotheses: The study sample will be recruited during the study timeline and a  $\geq 85\%$  follow-up rate will be attained. Coded intervention samples will meet benchmarks for proficiency on a validated treatment fidelity rating tool. Participants will report high satisfaction with the intervention.

**Aim 2: Examine the preliminary effectiveness of the intervention on well-being, shame, shame resilience, and treatment attendance.** We administer a battery of validated questionnaires at baseline and 1-month follow-up. We will analyze within-group changes in effectiveness outcome variables. Standardized measures of effect size will be calculated.

Hypotheses: The intervention will lead to significant improvements in well-being, shame, shame resilience, and treatment attendance.

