### **3. Study Design**

**3.3.** This project will use a mixed methods research design to determine the feasibility and impact of a brief, MI-Guided Shame Resilience intervention on well-being, shame intensity, shame resilience, willingness to communicate, and

treatment attendance. Data will be collected in person by survey and interview at baseline and either in-person or over the phone at 1-month follow-up. Although a controlled, between group design was considered for the current study, in consultation with Co-Investigators and Milagro providers and staff, we elected to conduct a within groups evaluation, to maximize our ability to refine and investigate the acceptability of the intervention. Within group changes in outcomes can be used to estimate effect sizes for a larger trial.

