#### **5. Number of Subjects**

**5.1** This is not a multi-center study.

**5.2** We will recruit participants at the South-East Heights Clinic and the FCM Clinic

We will recruit 20 participants for the pilot study.

**5.3** The sample size for this pilot study is based on the criteria set forth by [name] in 1995. The South-East Heights and FCM clinics provides health services to the Milagro population.

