Brief-Intervention: Twenty participants will receive a brief, MI-Guided Shame Resilience intervention. Participants will attend a one-on-one intervention with the research coordinator. The intervention will be 20-30 minutes and will be conducted in style consistent with MI. Participants will be invited to discuss their own experience with shame and how it affects them before moving into a collaborative discussion in which shame resilience strategies are introduced and practiced. The interventionist will help guide the conversation and incorporate shame resilience into the participants' own life.

All participants will receive the brief-intervention as there currently no alternative treatments or procedures for issues of shame.

Follow-up Data Collection: Telephone or in-person follow-up surveys at one month after receiving the intervention. In-person follow-ups will occur at a patients' scheduled visit to the clinic. Data collection will be surveys completed on a tablet device for privacy and security. If follow-up occurs over the phone, the interventionist will work with the participant to establish an adequate time, during the initial visit.

**12.3** We are not collecting existing or prospective data.

**12.4** Participant recruitment, consent, baseline measurements, and intervention will occur at the South East Heights clinic. Participant follow-up will occur over the phone or at the South East Heights Clinic. Data analysis will occur at the department of Family and Community Medicine.

**12.5** After completing the informed consent process participants will complete five instruments before the intervention to measure the preliminary effectiveness of the intervention. Participants will complete the instruments again during the 1-month follow-up phone call.

1. The *Measure of Subjective Well-Being* is short, five-item survey with Likert response options for subjective quality of life based on positive mood, vitality, and general interest. The tool was developed by the World Health Organization and has strong psychometric characteristics.

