To address Aim 2: Within group changes in targeted outcomes including well-being, shame, shame resilience, willingness to communicate about health, and treatment attendance. We will analyze the within-group data using one sample t-tests comparing baseline and follow-up means for each measure. In addition, we will calculate standardized effect sizes comparing baseline and follow-up scores, using Cohen's d. Exploratory analyses will compare all measures using a correlation matrix at both baseline and follow-up, particularly looking at the interaction between shame resilience and each measure.

Fidelity and Quality: The research coordinator will meet with the study PI, a clinical psychologist, weekly for clinical supervision during the intervention phase of the study. All sessions will be audio-recorded and scored by the PI using an established MI fidelity rating tool called the Motivational Interviewing Treatment Integrity Scale 4.2.1.

**13.4** The main purpose of this Pilot is to assess feasibility for a future clinical trial. Data from this pilot will be used in a future power analysis.

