## **19 Potential Benefits to Subjects**

**19.1** Participants involved in the study will receive a brief intervention in addition to standard care and may benefit from the effects of either. However, no proven direct health benefits will accrue to the research participants. If this research is successful, then the patients may benefit from new program developments based on the findings, but this is in the future.

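### Aim 2 predicts that the intervention will cause significant improvement, but the only analysis is a before-after test in one treated group, which cannot attribute change to the intervention.

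*Combined protocol and SAP*

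**What the plan says.** The Aim 2 hypothesis in section 1 is: "The intervention will lead to significant improvements in well-being, shame, shame resilience, and treatment attendance". It names four outcomes. Section 13.3 analyses those four and adds willingness to communicate about health. The analysis is a one-sample t-test of baseline against one-month follow-up for each measure, with Cohen's d. No alpha level, sidedness or multiplicity rule is given.

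There is no comparison group. Section 12.2 says "All participants will receive the brief-intervention as there currently no alternative treatments or procedures for issues of shame". Section 3.3 records that a controlled design was considered and then "we elected to conduct a within groups evaluation, to maximize our ability to refine and investigate the acceptability of the intervention". The same section proposes within-group change as a source of effect sizes for a larger trial, and section 13.4 sends the pilot data to a future power analysis.

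Two passages temper the claim. Section 13.4 states "The main purpose of this Pilot is to assess feasibility for a future clinical trial". Section 19.1 says participants "will receive a brief intervention in addition to standard care and may benefit from the effects of either".

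On size, section 5 says "We will recruit 20 participants for the pilot study", and Aim 1 predicts that at least an 85% "follow-up rate will be attained".

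**The concern.** The hypothesis is causal and is judged by statistical significance. The test can show only whether the group mean differs from baseline. Over one month several things can move that mean without any intervention effect: time in prenatal care and medication assisted treatment (an inclusion criterion), answering the same self-report instruments twice, and regression to the mean. The protocol gives no expected untreated change against which to judge the result, and nowhere limits what a significant change may be taken to mean.

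The causal reading has planned uses. Section 2.2 says data on feasibility and initial efficacy are needed to secure a larger grant. Section 3.3 would use the within-group change for effect sizes, and section 28.2 plans publication. A before-after effect size mixes intervention effect with background change. Carried into a controlled trial, where background change occurs in both arms, it could lead to the wrong sample size.

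**Working it through.** **The plan's own figure.** The sample size is 20. Section 5.3 says "The sample size for this pilot study is based on the criteria set forth by" a 1995 source and gives no effect size, SD, alpha or power, so 20 cannot be re-derived. That is ordinary for a pilot and is not counted as an error. The retention target gives 0.85 × 20 = 17 analysable participants.

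**Assumptions not in the documents.**
- The test is two-sided at 5%, so 2.5% lies in the favourable direction.
- The true intervention effect is zero.
- Favourable background change is δ = 0, 0.2, 0.3 or 0.4 SD of the differences.
- Changes on the outcomes are either independent or correlated at 0.5.

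**One outcome.** The chance of a significant improvement is P(T > t₀.₉₇₅,ₙ₋₁), where T is noncentral t with n − 1 degrees of freedom and noncentrality δ√n. The critical values are 2.120 (n = 17) and 2.093 (n = 20).

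| δ | n = 17 | n = 20 |
|---|---|---|
| 0 | 2.5% | 2.5% |
| 0.2 | 11.8% | 13.4% |
| 0.3 | 21.3% | 24.7% |
| 0.4 | 34.1% | 39.7% |

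**The four hypothesised outcomes, n = 17.** The plan does not say whether one, some or all must improve, so both extremes are shown.
- *At least one, independent:* 1 − (1 − 0.118)⁴ = 40% at δ = 0.2, and 1 − (1 − 0.341)⁴ = 81% at δ = 0.4.
- *At least one, correlation 0.5 (simulated, 200,000 runs):* about 30% at δ = 0.2 and 65% at δ = 0.4.
- *All four, independent:* 0.118⁴ = 0.02% and 0.341⁴ = 1.4%.
- *All four, correlation 0.5 (same simulation):* about 1% and 9%.

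**Smallest change that can be significant.** The observed mean change must reach t/√n SD of the differences: 2.120/√17 = 0.51 at n = 17, and 2.093/√20 = 0.47 at n = 20. A significant result therefore overstates any true change smaller than that. The same figures are the half-widths of the 95% confidence interval for the mean change, in SDs of the differences.

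**What the within-group effect size carries forward.** In these units its expected size is roughly intervention effect plus background change. With an effect of zero and background change of 0.2 to 0.4, the pilot would pass on about 0.2 to 0.4 where the between-group value is zero.

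**Would a control arm be the better repair?** Split 10:10, a true difference of 0.5 SD gives noncentrality 0.5 × √5 = 1.118 on 18 degrees of freedom, and power of about 18%. For 80% power, 2 × (1.960 + 0.842)² / 0.5² = 62.8, or 63 per arm. That is a different study.

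**The case against.** The strongest reply is that this is a 20-person pilot that already shows caution. Aim 2 is labelled preliminary effectiveness, a controlled design was considered and declined with reasons, feasibility is the stated main purpose, and section 19.1 claims no proven direct health benefit. A directional hypothesis does not oblige the sponsor to publish a causal conclusion. All of this stands as a defence of the design. It does not repair the hypothesis, because none of those statements says how a significant before-after change should be read.

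Four stronger readings are tempting, and the documents do not support them.
- A reader might infer that the plan has a success criterion under which an inert intervention would be declared effective. It has a hypothesis and t-tests, but no effectiveness rule, alpha level or go/no-go decision tied to Aim 2.
- A reader might count all five outcomes in section 13.3 as independent and take the chance of at least one significant result as 47% to 88%. The hypothesis names four outcomes. Sections 2.1 to 2.3 link shame and shame resilience with well-being, so independence gives only an upper bound.
- A reader might say that a significant result necessarily overstates the change. That holds only when the true change is below about 0.5 SD of the differences.
- A reader might assume that background change must flatter the intervention. It could be zero, or unfavourable, in which case it would hide a benefit.

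**Conclusion.** The concern holds as a mismatch between the Aim 2 hypothesis and the analysis, not as a fault in the single-arm design. A significant before-after change in this group cannot be attributed to the intervention. That conclusion rests on the text alone and on none of the assumed figures.

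The size of the risk does rest on assumptions. At n = 17 an inert intervention would reach significance on a given outcome with probability 2.5% with no background change, rising to 34% at 0.4 SD. With 0.2 to 0.4 SD of background change, the chance for the four hypothesised outcomes ranges from about 1% to 9% (all four, correlation 0.5), through 30% to 65% (at least one, correlation 0.5), to 40% to 81% (at least one, independent). The documents give no figure for one-month change under standard care, so these are illustrations, not predictions. The study remains sound for feasibility. The wording should be corrected before the effectiveness results are reported or used for planning.

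**What to change.** Three changes of wording:

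1. **Section 1, Aim 2.** Replace the hypothesis with an estimation aim: estimate the change from baseline to 1 month in each outcome, with a 95% confidence interval. Remove the statement that the intervention will produce significant improvement.
2. **Section 13.3.** State that observed changes may reflect time, standard care or repeat measurement and are not attributed to the intervention.
3. **Sections 3.3 and 13.4.** State that the within-group Cohen's d will not be used directly as the between-group effect size in the future power analysis. The SDs and the retention rate can be used.

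No new go/no-go rule is needed for this point. Enrolment, procedures, data collection and the sample size of 20 are unaffected. The cost is that the stated claim becomes less favourable.

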## 2. Background

2.1 While the emotion of guilt entails "feeling bad" about a choice, shame involves the internalization of this emotion to a feeling of "I am bad." While both emotions likely serve an adaptive function in helping individuals to modify behaviors, because of its internalized nature, shame is also often associated with negative behavioral health outcomes, and, based on our own preliminary data, lower overall well-being. Specific to the current application, individuals who misuse substances have been found to have high levels of shame and women often experience shame during pregnancy, particularly when there is a history of sexual or other trauma. The stigma associated with drug use during pregnancy is particularly high and leads to extensive shame among affected patients.

Although it is difficult to estimate the prevalence of substance misuse during pregnancy because of the impact of shame on willingness to report accurately, available data suggests that more 5% of women report use drugs during pregnancy. Nationally, more

than ten thousand infants are born to opioid addicted mothers each year. New Mexico is among the highest with rates of pregnant opioid misuse exceeding 2.5 per 1000 deliveries. The impact of substance use on the health of pregnant women and their fetuses is a significant public health concern. Opioid use during pregnancy can lead to preterm births, poor fetal growth, longer hospital stays, and birth defects. Opioid misuse during pregnancy can also lead to neonatal abstinence syndrome (NAS). NAS is a drug withdrawal syndrome that affects opioid-exposed infants shortly after birth. NAS can lead to respiratory complications, feeding difficulties, and seizures and accounts for upwards of half of all neonatal intensive care hospital unit stays.

Shame has been found to function as a major barrier to care across a range of health behaviors. This effect is especially evident in populations of women dealing with stigmatized health issues, such as HIV/AIDS, depression, eating disorders, and domestic violence. Shame has been found to decrease the chance that patients will attend care and disclose unhealthy behavior to practitioners. For women who use substances during pregnancy, shame has been found to negatively impact participation and engagement in care, as it motivates efforts to avoid detection by not attending care, limits disclosure to providers, and decreases acceptance of front line recommended medication assisted treatments.

Despite the well documented impacts of shame on health outcomes, little empirical work has investigated interventions that may minimize shame or its negative impacts on health. Intervention development and evaluation could be guided by the prominent Shame Resilience Theory. Shame Resilience Theory posits that four behaviors may minimize the negative impact of shame on health outcomes, by improving understanding and encouraging vulnerability. These include:

- 1) Seeking to Understand Shame - Shame is an emotion that is often mistaken for other emotions. Shame can be difficult to identify and process, as the feelings of shame is often misattributed to other emotional processes. This behavior involved identifying shame as well as shame triggers.
- 2) Practicing Critical Awareness – This behavior serves to improve understanding and involves efforts to normalize and contextualize the thoughts coming from the shame response and process them.
- 3) Reaching Out – This behavior involves disclosing shame to others and asking for empathy from a support network.
- 4) Speaking Shame – This behavior involves speaking openly about the experience of shame and leading to desensitization and externalization.

Shame Resilience Theory was developed through qualitative interviewing techniques and has not been translated into a replicable behavioral health intervention or qualitatively evaluated to determine its impact on health outcomes.

One means by which Shame Resilience Theory could be translated into clinical practice is through a widely utilized and evidence-based communication strategy known as Motivational Interviewing (MI). MI is a collaborative, goal-oriented style of communication with particular attention to the language of change. It is designed to strengthen personal motivation for and commitment to a specific goal by eliciting and exploring a person's own reasons for change within an atmosphere of acceptance and compassion. MI is often implemented as a brief intervention in medical settings. In the current study, we seek to use MI as a

communication strategy to encourage behaviors thought to minimize the impact of shame on health as posited by Shame Resilience Theory. The goal of the current research is to evaluate the feasibility and preliminary effectiveness of an MI-Guided Shame Resilience intervention with pregnant, opioid misusing women attending UNM's Milagro Treatment Programs. Identifying an effective and scalable intervention for managing shame in these settings, holds promise for significantly improving engagement in care, and consequent mother and fetus outcomes.

**2.2** The PI has dedicated her career to the development and evaluation of brief applications of MI, including a clinical trial focused on risky alcohol use in a recently completed K23 award (K23 AA020865;) and another soon to be completed multi-site clinical trial focused on unintended pregnancy prevention from an R01 level grant (TP2AH000028;). The current proposal bridges the PI's background in addictions and pregnancy and targets a new health behavior in shame resilience. Pilot data demonstrating feasibility and initial efficacy will be needed in order to secure a larger grant. Co-Investigator [name] is the Medical Director of the Milagro Clinic. He will shortly be conducting a sabbatical at X in which he will be focusing on treatments for shame and trauma with this clinical population. He has previously worked on treating infants who were exposed to substances during pregnancy as well as researching treatment programs of pregnant women with past trauma and substance abuse. Project Coordinator, [name], also has extensive experience relevant to shame resilience and motivational interviewing, making him ideal to carry out the study intervention and evaluation aspects of the proposal. [name] recently graduated with honors from UNM's psychology department, where his senior thesis, which is currently under review for publication found a significant association between shame resilience and well-being, providing support for the theoretical mechanisms underlying shame resilience theory. [name] has worked extensively with the PI for the past year and is skill MI interventionist.

**2.3.** [name] recently graduated with honors from UNM's psychology department, where his senior thesis, which is currently under review for publication found a significant association between shame resilience and well-being, providing support for the theoretical mechanisms underlying shame resilience theory.

**2.4.** Based on the existing literature this research is the next reasonable step in establishing the efficacy of the shame resilience theory. To our knowledge this is the first shame resilience intervention to be established and examined. This project will add to the current literature by expanding our knowledge of shame and by providing quantitative evidence to the leading theory of managing shame. Continuing research with a pilot study is important to evaluate and formulate the intervention as well as how the intervention is administered. Participant feedback will be important in finalizing the intervention for a future clinical trial. A smaller group will allow for both quantitative and qualitative data. Allowing us to incorporate measurable changes and participant suggestions.

